13.3. Appendix 3: Assessment Windows**13.3.1. Definitions of Assessment Windows for Analyses**

Analyses will be presented by scheduled visits as collected in the CRF. The following table presents protocol defined assessment windows.

Part 1

Analysis Set / Domain	Parameter (if applicable)	Target	Analysis Window		Analysis Timepoint
			Beginning Timepoint	Ending Timepoint	
Safety and Efficacy	All	14 - 28 days prior to first dose	28 days prior to first dose	Day -1	Screen
Efficacy	HIV-1 RNA, HIV-1 genotype / phenotype	Day 1	Day 1	Day 1	Visit 1
		Day 2	Day 2	Day 2	Visit 2
		Day 3 or 4	Day 3	Day 4	Visit 3
		Day 5, 6, or 7	Day 5	Day 7	Visit 4
		Day 8, 9, or 10	Day 8	Day 10	Visit 5
		Day 11	Day 11	Day 11	Visit 6
		Day 12	Day 12	Day 12	Visit 7
		Day 13, 14, 15, 16, or 17	Day 13	Day 17	Visit 8
		Days 18 to final follow up visit day	Day 18	final follow up visit day	Follow-up
	CD4 and CD8	Day 1	Day 1	Day 1	Visit 1
Day 11		Day 11	Day 11	Visit 6	
Safety	Laboratory: Chemistry/ Haematology/ Urinalysis	Day 1	Day 1	Day 1	Visit 1
		Day 2	Day 2	Day 2	Visit 2
		Day 3 or 4	Day 3	Day 4	Visit 3
		Day 5, 6, or 7	Day 5	Day 7	Visit 4
		Day 8, 9, or 10	Day 8	Day 10	Visit 5
		Day 11	Day 11	Day 11	Visit 6
		Days 18 to final follow up visit day	Day 18	final follow up visit day	Follow-up
	Fasting Lipid Panel	Day 1	Day 1	Day 1	Visit 1
		Day 11	Day 11	Day 11	Visit 6
		Days 18 to final follow up visit day	Day 18	final follow up visit day	Follow-up
	ECG	Day 1 ¹	Day 1	Day 1	Visit 1
		Day 2 ²	Day 2	Day 2	Visit 2
		Day 3 or 4 ²	Day 3	Day 4	Visit 3
Day 8, 9, or 10 ³		Day 8	Day 10	Visit 5	
Days 18 to final follow up visit day ²		Day 18	final follow up visit day	Follow-up	

CONFIDENTIAL

208132

Analysis Set / Domain	Parameter (if applicable)	Target	Analysis Window		Analysis Timepoint
			Beginning Timepoint	Ending Timepoint	
	Vital Signs	Day 1	Day 1	Day 1	Visit 1
		Day 2	Day 2	Day 2	Visit 2
		Day 3 or 4	Day 3	Day 4	Visit 3
		Day 8, 9, or 10	Day 8	Day 10	Visit 5
		Days 18 to final follow up visit day	Day 18	final follow up visit day	Follow-up

NOTES:

¹ 12-lead ECG (triplicate reading, pre-dose; single readings at PK draws 2hr, 4hr, and 6hr)

² 12-lead ECG (single reading, pre-dose)

³ 12-lead ECG (single reading pre-dose and at PK draws 2hr, 4hr, and 6hr)

Part 2

Analysis Set / Domain	Parameter (if applicable)	Target	Analysis Window		Analysis Timepoint
			Beginning Timepoint	Ending Timepoint	
Safety and Efficacy	All	14 - 28 days prior to first dose	28 days prior to first dose	Day -1	Screen
Efficacy	HIV-1 RNA, HIV-1 genotype / phenotype	Day 1	Day 1	Day 1	Visit 1
		Day 2	Day 2	Day 2	Visit 2
		Day 3 or 4	Day 3	Day 4	Visit 3
		Day 5 or 6	Day 5	Day 6	Visit 4
		Day 7	Day 7	Day 7	Visit 5
		Day 8	Day 8	Day 8	Visit 6
		Days 10 to final follow up visit day	Day 10	final follow up visit day	Visit 7
	CD4 and CD8	Day 1	Day 1	Day 1	Visit 1
		Day 8	Day 8	Day 8	Visit 6
	Safety	Laboratory: Chemistry/ Haematology/ Urinalysis	Day 1	Day 1	Day 1
Day 2			Day 2	Day 2	Visit 2
Day 3 or 4			Day 3	Day 4	Visit 3
Day 5 or 6			Day 5	Day 6	Visit 4
Day 7			Day 7	Day 7	Visit 5
Day 8			Day 8	Day 8	Visit 6
Days 10 to final follow up visit day			Day 10	final follow up visit day	Visit 7
Fasting Lipid Panel		Day 1	Day 1	Day 1	Visit 1
		Day 8	Day 8	Day 8	Visit 6
		Days 10 to final follow up visit day	Day 10	final follow up visit day	Visit 7
ECG		Day 1 ¹	Day 1	Day 1	Visit 1

CONFIDENTIAL

208132

Analysis Set / Domain	Parameter (if applicable)	Target	Analysis Window		Analysis Timepoint
			Beginning Timepoint	Ending Timepoint	
		Day 2 ²	Day 2	Day 2	Visit 2
		Day 3 or 4 ²	Day 3	Day 4	Visit 3
		Day 7 ³	Day 7	Day 7	Visit 5
		Days 10 to final follow up visit day	Day 10	final follow up visit day	Visit 7
	Vital Signs	Day 1	Day 1	Day 1	Visit 1
		Day 2	Day 2	Day 2	Visit 2
		Day 3 or 4	Day 3	Day 4	Visit 3
		Day 7	Day 7	Day 7	Visit 5
		Days 10 to final follow up visit day	Day 10	final follow up visit day	Visit 7

NOTES:

¹ 12-lead ECG (triplicate reading, pre-dose; single readings at PK draws 2hr, 4hr, and 6hr)

² 12-lead ECG (single reading, pre-dose)

³ 12-lead ECG (single reading pre-dose and at PK draws 2hr, 4hr, and 6hr)

CONFIDENTIAL

208132

13.4. Appendix 4: Study Phases and Treatment Emergent Adverse Events**13.4.1. Study Phases**

Assessments and events will be classified according to the time of occurrence relative to the start and/or stop date of the study treatment.

Study Phase	Definition
Screening Period	Day -28 to Day -1
Treatment Period	Day 1 to Day 10 / study treatment stop date in Part 1 and Day 1 to Day 7 / study treatment stop date in Part 2
Follow-up Period	Study treatment stop date + 1 to Day 24 in Part 1 and study treatment stop date + 1 to Day 12 in Part 2

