A qualified participant will be randomized into the treatment phase of the study and will administer study treatments, once daily, from Day 1 through Day 10 in Part 1 and from Day 1 through Day 7 in Part 2. On Day 1, an appropriate number of bottles will be dispensed, with a supply sufficient to cover the entire treatment period. The blinded bottles will contain capsules of either the active dose or placebo. Dosing instructions will be indicated on each bottle. Participants will bring the bottles of study treatments to each visit, so that study treatment can be administered in the clinic after the study procedures have been performed.

Each dose of study medication will be taken with approximately 240 mL (8 ounces) of water following ingestion of a moderate calorie and fat meal (i.e. at least 400 calories, with at least 120 calories from fat), that is required to be completed within 30 minutes prior to dosing. A moderate calorie and fat breakfast is planned to be similar to the following (additional meal suggestions will be included in the Study Reference Manual [SRM]):

- 2 slices of bread
- 10 g of butter
- 20 g of jam
- 15 g of cheese
- 175 mL of apple juice

Study treatments should be administered near the same time each morning, within a 2-hr window.

On days when the participant self-administers the study treatments, observed dosing with a site staff member may be achieved as locally permitted using various forms of video calling (when at all possible) such as FaceTime, Skype, WhatsApp.

Participants will then enter the post-dosing period:

Study Part 1:

There are 4 in-clinic visits in the Part 1 post-dosing period: 3 visits for PK and other assessments during the 7 days immediately following the last dose, and a final follow-up visit primarily for safety (e.g., to follow any AEs to resolution) approximately 8-14 days after the last dose, as shown in the Part 1 Schedule of Activities (SOA, Section 2). In Part 1, participants should not start other medicines and will not start ARVs during the post-dosing period until they have completed the final follow-up visit.

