	Day 1	Day 2	Day 3, 4 Choose one day for the Clinic Visit 3. The other day will be a virtual event.		Day 5, 6, 7 Choose one day for the Clinic Visit 4. The other days will be virtual events.			Day 8, 9, 10 Choose one day for the Clinic Visit 5. The other days will be virtual events.			Day 11	Day 12	Day 13, 14, 15, 16 or 17	Day 18, 19, 20, 21, 22, 23 or 24
	Clinic Visit 1	Clinic Visit 2	Clinic Visit 3	Virtual	Clinic Visit 4	Virtual	Virtual	Clinic Visit 5	Virtual	Virtual	Clinic Visit 6	Clinic Visit 7	Clinic Visit 8	Clinic Visit 9
Clinical Procedures														
12-lead ECG (triplicate reading, pre-dose; single readings at PK draws 2hr, 4hr, and 6hr)	X													
12-lead ECG (single reading, pre-dose at Visits 2 and 3)		X	X											X
12-lead ECG (single reading pre-dose and at PK draws 2hr, 4hr, and 6hr)								X						
Pharmacogenetics (PGX) Collection (if consented)	X													

Procedure ¹	Treatment Period Day 1 – Day 10									Post-Dosing Follow Up Period Day 11 – 17			Final Follow-up Day 18-24	
	Day 1	Day 2	Day 3, 4 Choose one day for the Clinic Visit 3. The other day will be a virtual event.		Day 5, 6, 7 Choose one day for the Clinic Visit 4. The other days will be virtual events.			Day 8, 9, 10 Choose one day for the Clinic Visit 5. The other days will be virtual events.			Day 11	Day 12	Day 13, 14, 15, 16 or 17	Day 18, 19, 20, 21, 22, 23 or 24
	Clinic Visit 1	Clinic Visit 2	Clinic Visit 3	Virtual	Clinic Visit 4	Virtual	Virtual	Clinic Visit 5	Virtual	Virtual	Clinic Visit 6	Clinic Visit 7	Clinic Visit 8	Clinic Visit 9
Hematology/Chem istry/Urine	X	X	X		X			X			X			X
Fasting Lipid Panel (approximately 8 hrs)	X										X			X
Lymphocyte T-cell subsets (CD4, CD8)	X										X			
Plasma for HIV-1 genotype/phenoty pe ⁵	X	X	X		X			X			X	X	X	X
Plasma for storage ⁶	X	X	X		X			X			X	X	X	X
HIV-1 RNA	X	X	X		X			X			X	X	X	X

Procedure ¹	Treatment Period Day 1 – Day 10									Post-Dosing Follow Up Period Day 11 – 17			Final Follow-up Day 18-24	
	Day 1	Day 2	Day 3, 4 Choose one day for the Clinic Visit 3. The other day will be a virtual event.		Day 5, 6, 7 Choose one day for the Clinic Visit 4. The other days will be virtual events.			Day 8, 9, 10 Choose one day for the Clinic Visit 5. The other days will be virtual events.			Day 11	Day 12	Day 13, 14, 15, 16 or 17	Day 18, 19, 20, 21, 22, 23 or 24

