7.1. Primary Efficacy Analyses

7.1.1. Endpoint / Variables

- Change from baseline to the nadir (maximum change from baseline) in Plasma HIV-1 RNA
- Change from baseline to Visit 6 (Day 11 in Part 1 and Day 8 in Part 2) in Plasma HIV-1 RNA

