1. Details of liver chemistry stopping criteria and required actions and follow-up assessments after liver stopping or monitoring event are given in Section 8.1 and Appendix 7 All events of ALT $\geq 3 \times$ upper limit of normal (ULN) and bilirubin $\geq 2 \times$ ULN (>35% direct bilirubin) or ALT $\geq 3 \times$ ULN and international normalized ratio (INR) >1.5 , if INR measured, which may indicate severe liver injury (possible Hy's Law), must be reported as an SAE (excluding studies of hepatic impairment or cirrhosis).
2. Local urine testing will be standard for the protocol unless serum testing is required by local regulation or IRB/IEC.

Laboratory values, treatment emergent toxicities, and change from baseline for haematology, clinical chemistry, and liver function parameters will be summarized by visit and by treatment group. Laboratory values for haematology, clinical chemistry, liver function, and urinalysis will also be listed by subject. In addition, the number and percentage of participants with on-treatment laboratory abnormalities worsened from baseline by maximum grade will be reported for haematology, clinical chemistry. The participants with laboratory values of potential clinical importance will be summarised and listed (potential clinical importance criteria are specified in Section 13.8). The details of the planned displays are in Appendix 11: List of Data Displays.

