13.11.7. Safety Tables

Safety: Tables					
No.	Population	IDSL / Example Shell	Title	Programming Notes	Deliverable [Priority]
Adverse Events (AEs)					
3.1.	Safety	AE13	Adverse Events Overview		SAC
3.2.	Safety	AE1	Summary of All Adverse Events by System Organ Class and Preferred Term	ICH E3	HL, SAC
3.3.	Safety	AE5B	Summary of All Adverse Events by System Organ Class and Preferred Term and Maximum Grade	ICH E3	SAC
3.4.	Safety	AE3	Summary of Common ($\geq 5\%$) Adverse Events by Preferred Term	ICH E3	SAC
3.5.	Safety	AE15	Summary of Common ($\geq 5\%$) Non-serious Adverse Events by Preferred Term (Number of Subjects and Occurrences)	FDAAA, EudraCT	SAC
3.6.	Safety	AE1	Summary of All Drug-Related Adverse Events by System Organ Class and Preferred Term	ICH E3	HL, SAC
3.7.	Safety	AE5B	Summary of All Drug-Related Adverse Events by System Organ Class and Preferred Term and Maximum Grade	ICH E3	SAC
3.8.	Safety	AE1	Summary of Adverse Events of Special Interest		SAC
Serious and Other Significant Adverse Events					
3.9.	Safety	AE16	Summary of Serious Adverse Events by System Organ Class and Preferred Term (Number of Participants and Occurrences)	FDAAA, EudraCT	SAC
3.10.	Safety	AE1	Summary of Adverse Events Leading to Permanent Discontinuation of Study Treatment or Withdrawal from Study by System Organ Class and Preferred Term	IDSL	SAC

CONFIDENTIAL

208132

Safety: Tables					
No.	Population	IDSL / Example Shell	Title	Programming Notes	Deliverable [Priority]
Laboratory: Chemistry					
3.11.	Safety	LB1	Summary of Clinical Chemistry Data by Visit – Part 1	ICH E3	SAC
3.12.	Safety	LB1	Summary of Clinical Chemistry Data by Visit – Part 2	ICH E3	SAC
3.13.	Safety	LB1	Summary of Changes from Baseline in Clinical Chemistry Data by Visit – Part 1	ICH E3	SAC
3.14.	Safety	LB1	Summary of Changes from Baseline in Clinical Chemistry Data by Visit – Part 2	ICH E3	SAC
3.15.	Safety	LB18	Summary of Worst-Case Chemistry Grade Shifts from Baseline Grade – Part 1	ICH E3 Display only worst case post baseline visits.	HL, SAC
3.16.	Safety	LB18	Summary of Worst-Case Chemistry Grade Shifts from Baseline Grade – Part 2	ICH E3 Display only worst case post baseline visits.	HL, SAC
3.17.	Safety	LB17	Summary of Chemistry Laboratory Abnormalities of Potential Clinical Importance – Part 1		SAC
3.18.	Safety	LB17	Summary of Chemistry Laboratory Abnormalities of Potential Clinical Importance – Part 2		SAC

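### The SAP gives two laboratory windows for the maximum-grade tables: one omits Visit 6 and every post-baseline lipid panel, the other takes in Part 2 draws made after cART starts

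*SAP*

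**What the plan says.** SAP 13.4.1 states the general rule: "Assessments and events will be classified according to the time of occurrence relative to the start and/or stop date of the study treatment". The Treatment Period is "Day 1 to Day 10 / study treatment stop date in Part 1 and Day 1 to Day 7 / study treatment stop date in Part 2" and the Follow-up Period is "Study treatment stop date + 1 to Day 24 in Part 1 and study treatment stop date + 1 to Day 12 in Part 2". Neither has a lag after the last dose.

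The protocol synopsis has study treatment taken "once daily, from Day 1 through Day 10 in Part 1 and from Day 1 through Day 7 in Part 2". SAP 7.1.1 fixes the day of Visit 6 in one of its endpoints: "Change from baseline to Visit 6 (Day 11 in Part 1 and Day 8 in Part 2) in Plasma HIV-1 RNA".

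SAP 8.3 says that "the number and percentage of participants with on-treatment laboratory abnormalities worsened from baseline by maximum grade will be reported", for haematology and clinical chemistry. The same section lists the fasting lipid panel under clinical chemistry.

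The display list in SAP 13.11.7 uses another window for the chemistry grade-shift tables (3.15 and 3.16): "Display only worst case post baseline visits". The haematology counterparts (3.25 and 3.26) carry no window note. Nor do the treatment-emergent toxicity tables (3.19, 3.20, 3.29, 3.30, 3.41 and 3.42). The treatment-emergent flag in SAP 13.4.2 is for adverse events only and runs to the final follow-up visit.

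**The concern.** A programmer building the maximum-grade tables has to choose between two windows, and neither gives a clean table.

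Under the text of 8.3 with the phases of 13.4.1, the last draw counted is the pre-dose sample at Visit 5. The end-of-treatment sample drops out, and no post-baseline lipid value can contribute. Under the display note, Visit 6 counts, but so does Part 2 Visit 7. By then participants are taking investigator-selected cART, so a worst grade could reflect the study drug, cART or both. Part 1 participants start no ARVs until after final follow-up, so the same table would mean different things in the two parts.

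At stake is how the tables that summarise worst laboratory toxicity by dose are read. No hypothesis test depends on them.

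**Working it through.** The plan gives no figure to reproduce. The check maps each scheduled draw to the phases of SAP 13.4.1.

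**Inputs**
- Last dose: Day 10 in Part 1, Day 7 in Part 2 (protocol synopsis).
- Draw days: SAP Appendix 3, which agrees with the schedules in protocol 2.2.
- Blood is drawn before dosing (footnote 1 to the schedules), so the Day 1 sample is the baseline and is not counted as on-treatment.

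**Mapping for completers**

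| Test | Part | Post-baseline draws | Day ≤ stop date | Day ≤ stop date + 1 |
|---|---|---|---|---|
| Chemistry/haematology | 1 | Visits 2, 3, 4, 5, 6 and follow-up (6) | Visits 2–5: 4 of 6 | Visits 2–6: 5 of 6 |
| Chemistry/haematology | 2 | Visits 2, 3, 4, 5, 6, 7 (6) | Visits 2–5: 4 of 6 | Visits 2–6: 5 of 6 |
| Fasting lipids | 1 | Day 11, Day 18–24 (2) | 0 of 2 | 1 of 2 |
| Fasting lipids | 2 | Day 8, Day 10–12 (2) | 0 of 2 | 1 of 2 |

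Visit 6 is Day 11 = 10 + 1 in Part 1 and Day 8 = 7 + 1 in Part 2. The lipid result is the same in all five active arms and both placebo groups.

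**Doses taken before the last counted draw.** With phases as written, this is the pre-dose Visit 5 sample. In Part 1 it falls on Day 8, 9 or 10, after 7, 8 or 9 of 10 doses. In Part 2 it falls on Day 7, after 6 of 7 doses.

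**Exposure at Visit 6.** Protocol 3.2.2 gives a mean half-life of about 22 to 29 hours on repeat dosing. Assuming simple exponential decline, the fraction remaining after 24 hours is 0.5^(24/half-life):
- 22 hours: 0.5^(24/22) = 0.469
- 29 hours: 0.5^(24/29) = 0.563

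Protocol Table 2 agrees. Predicted C24/Cmax is 30/61 = 0.492 at 5 mg and 809/1629 = 0.497 at 200 mg. Visit 6 is thus a sample at the end of the final dosing interval, not after washout.

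**The other window.** All post-baseline visits means 6 of 6 and 2 of 2. In Part 2 this includes Visit 7 on Day 10–12, which is 2 to 4 days after cART starts on Day 8. The Day 8 blood is drawn before the first cART dose (protocol 5.1.1.2 and 7.8), so Visit 6 itself carries no cART effect.

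**The case against.** The strongest reply is that the omission is inferred. SAP 8.3 does not cite Appendix 4, and 13.4.1 defines a Treatment Period without defining on-treatment for laboratory data. SAP 8.3 sends the reader to the display list, where no laboratory table is titled or annotated as on-treatment. If the display list governs, Visit 6 counts. Ending the treatment phase at the last dose also matches the protocol, which heads Day 11 and Day 8 as post-dosing follow-up. These points are sound and limit the size of the problem. They do not settle which window applies, and the display-list window has its own fault in Part 2.

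Four stronger readings are tempting, and the documents do not support them.
- **Visit 6 laboratory data are lost.** They are not. Values and changes from baseline are summarised by visit (Tables 3.11–3.14 and 3.21–3.24), and full data are listed (Listings 39–41).
- **Lipid abnormalities will be reported as none observed.** Nothing says how an empty row would be shown, and the question arises only if the 8.3 text prevails.
- **Visit 6 is the only draw after the full course.** Final follow-up is also after it. Visit 6 is the only one within a dosing interval of the last dose and, in Part 2, the only one before cART.
- **Visit 6 always falls on stop date + 1.** This holds for completers. Protocol 8.2 gives withdrawn participants a visit conducted as Visit 9 or Visit 7.

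It is also fair to say that simply cutting the worst-case tables at Visit 6 would remove the final follow-up draw, including a Part 1 draw free of ARVs. The remedy has to keep that draw visible.

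**Conclusion.** The inconsistency is real and should be resolved, but its reach is limited. SAP 8.3 with 13.4.1 gives 4 of 6 chemistry and haematology draws and 0 of 2 lipid panels after baseline. The note to Tables 3.15 and 3.16 gives all of them, including a Part 2 draw after cART. Tables 3.25 and 3.26 and the treatment-emergent toxicity tables state no laboratory window. Only these maximum-grade and treatment-emergent displays are affected; by-visit summaries and listings are not.

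The counts assume completers attending on schedule with a recorded stop date. For participants who stop early, no scheduled post-baseline lipid panel falls in the Treatment Period either. Their withdrawal visit (7–14 days after stopping in Part 1, 3–5 days in Part 2) lies outside a one-day extension as well. The case for counting Visit 6 as on-treatment rests on its timing. It is about 24 hours after the last dose, with roughly half the drug remaining if participants' half-life resembles that of healthy volunteers. Protocol 9.4.4 likewise extends its laboratory repeat rule to 2 days after the last dose.

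**What to change.** In SAP 8.3 and 13.4.1, define one laboratory window, for example: *for laboratory data, on-treatment runs from first dose through study treatment stop date + 1 day, which for completers includes Visit 6; in Part 2 the Day 8 sample precedes cART.*

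Apply it to Tables 3.15, 3.16, 3.25 and 3.26 and to the treatment-emergent toxicity tables, and change the note on 3.15 and 3.16 to match. Keep the final follow-up draw in a separate post-treatment worst-case row or column, labelled in Part 2 as after cART start, so that no late abnormality is lost.

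For completers, on-treatment lipid panels go from 0 to 1 of 2, and chemistry and haematology draws from 4 to 5 of 6, relative to the 8.3 reading.

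The cost is SAP wording, a one-day change in a derived flag, and one extra row or column per table. No new data are needed. On-treatment counts may rise relative to the 8.3 text, or fall relative to the current post-baseline note because follow-up moves to its own row or column. The SAP should say so.

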13.4.1.1. Study Phases for Concomitant Medication

Study Phase	Definition
Prior	If medication end date is not missing and is before 28 days prior to screening visit
Concomitant	Any medication that is not a prior

NOTES:

- Please refer to [Appendix 7: Reporting Standards for Missing Data](#) for handling of missing and partial dates for concomitant medication. Use the rules in this table if concomitant medication date is completely missing.

13.4.2. Treatment Emergent Flag for Adverse Events

Flag	Definition
Treatment Emergent	Study Treatment Start Date ≤ AE Start Date ≤ Final Follow-up Visit.

NOTES:

- If the study treatment stop date is missing, then the AE will be considered to be On-Treatment.
- Time of study treatment dosing and start/stop time of AEs should be considered, if collected.

CONFIDENTIAL

208132

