In the shortest course for Part 1, a participant can be screened/qualified, treated and assessed for all the planned visits (including the final follow-up visit) in approximately 30 days (if, for example, only 10-14 days are needed for the screening period and the final follow-up visit is performed on Day 18). In the longest course for Part 1, a participant can be screened/qualified, treated and assessed for all the planned visits (including the final follow-up visit) in 52 days (if, for example, 28 days are needed for the screening period and the final follow-up visit is performed on Day 24).

Study Part 2:

There are 2 in-clinic visits in the Part 2 post-dosing period: 1 visit for PK and other assessments on the day immediately following the last dose, and a final follow-up visit primarily for safety (e.g., to follow any AEs to resolution) 3-5 days after the last dose, as shown in the Part 2 Schedule of Activities (SOA, Section 2).

In Part 2, participants will start Investigator-selected, prescribed and provided cART immediately following the completion of the primary endpoint, i.e., the measurement of HIV-1 RNA on Day 8.

In the shortest course for Part 2, a participant can be screened/qualified, treated and assessed for all the planned visits (including the final follow up visit) in approximately 24 days (if, for example, only 10-14 days are needed for the screening period and the final follow-up visit is performed on Day 10). In the longest course, a participant can be screened/qualified, treated and assessed for all the planned visits (including the final follow-up visit) in 40 days (if, for example, 28 days are needed for the screening period and the final follow-up visit is performed on Day 12).

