5.1.1.2. Treatment Phase and Follow-up Period

Part 1:

Participants will be required to attend 9 in-clinic visits throughout the duration of the study in Part 1. Participant and Investigators will design a patient-centric visit schedule

based on the optionality presented in the Part 1 Schedule of Assessments (SOA; Section 2) to accommodate the 9 required visits over the (maximum) 24-day study period, and such that no visit interval exceeds more than 3 days.

Part 2:

Participants will be required to attend 7 in-clinic visits throughout the duration of the study in Part 2. Participant and Investigators will design a patient-centric visit schedule based on the optionality presented in the Part 2 Schedule of Assessments (SOA; Section 2) to accommodate the 7 required visits over the (maximum) 12-day study period, and such that no visit interval exceeds more than 3 days.

Treatment Phase: Day 1 – Day 10 in Part 1 and Day 1 – Day 7 in Part 2:

On Day 1, an appropriate number of bottles of study treatments will be dispensed with supply sufficient to cover the entire treatment period. The blinded bottles will contain capsules of either the active dose or placebo. Each bottle will indicate dosing instructions. Participants will bring the bottles of study treatments to each visit, so that they can be administered after the study procedures have been performed.

Participants will report to the clinic for visits in the morning of the days selected for each of the 5 visits in the treatment phase. Participants will arrive each day, with their study treatment container(s) and prior to administration of the morning dose, for safety and lab assessments, including ECGs and blood draws, as described in the SOA. Participants will be given morning doses in the clinic at each visit. On days when an in-clinic visit is not required, doses can be self-administered, and during observation by a site staff member using various forms of video calling (when at all possible and locally permitted) such as FaceTime, Skype, WhatsApp.

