Two, serial, intensive blood PK sample collections will be done on Clinic Visit 1 and on Clinic Visit 5 (up to 24 hours post-morning dose). Participants will be required to fast for at least 8 hours [overnight] prior to the morning check-in for the intensive PK sampling visits. Participants will be required to stay in the clinic until all specified assessments are completed (12 hours post-dose). Participants will be required to return to the clinic the following morning to allow for the blood sampling at the 24-hr time point.

Study treatments should be administered near the same time each morning, within a 2-hr window.

Each dose of study medication will be taken with approximately 240 mL (8 ounces) of water following ingestion of a moderate calorie and fat meal (i.e. at least 400 calories, with at least 120 calories from fat), that is required to be completed within 30 minutes just prior to dosing. A moderate calorie and fat breakfast is planned to be similar to the following (with additional meal suggestions in will be included in the Study Reference Manual [SRM]):

- 2 slices of bread
- 10 g of butter
- 20 gr of jam

- 15 g of cheese
- 175 mL of apple juice

Follow-up Visits

Part 1:

Follow-up Visits Day 11-17 and Final Follow-up Visit Day 18-24

Participants should not start other medicines and will not start ARVs during the post-dosing follow-up period until after the final follow-up visit has been completed.

Participants will return to the clinic in the post-dosing period for 4 visits (Visits 6-9).

- Three visits will be performed within the 7 days immediately following the dosing period for PK and measurement of assessments as shown in the SOA (Section 2).
- A final follow-up visit, to be performed approximately 8-14 days after the last dose, will be primarily for safety (e.g., to follow any AEs to resolution).

If a participant is unable to return to the clinic for any reason site staff are encouraged to contact the participant for assessment of adverse events.

Part 2:

Follow-up Visit Day 8 and Final Follow-up Visit Day 10-12

[figure not shown]
Participants should start Investigator-selected, prescribed and provided cART immediately in the post-dosing period on Day 8, after the blood collection is performed.

Participants will return to the clinic in the post-dosing period for 2 visits (Visits 6 and 7).

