9.2.1. Time Period and Frequency for Collecting AE and SAE Information

- All SAEs will be collected from the signing of the ICF until the final follow-up visit at the time points specified in the SOA (Section 2).
- All AEs will be collected from the start of treatment until the final follow-up visit at the time points specified in the SOA (Section 2).
- Medical occurrences that begin before the start of study treatment but after obtaining informed consent will be recorded on the Medical History/Current Medical Conditions section of the case report form (CRF) not the AE section.
- All SAEs will be recorded and reported to the sponsor or designee immediately and under no circumstance should this exceed 24 hours, as indicated in [Appendix 4](#). The investigator will submit any updated SAE data to the sponsor within 24 hours of it being available.
- Investigators are not obligated to actively seek AEs or SAEs in former study participants. However, if the investigator learns of any SAE, including a death, at any time after a participant has been discharged from the study, and he/she considers the event to be reasonably related to the study treatment or study participation, the investigator must promptly notify the sponsor.
- The method of recording, evaluating, and assessing causality of AEs and SAEs and the procedures for completing and transmitting SAE reports are provided in [Appendix 4](#).

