8.1. Adverse Events Analyses

Adverse events analyses including the analysis of adverse events (AEs), Serious (SAEs) and other significant AEs will be based on GSK Core Data Standards. The details of the planned displays are provided in [Appendix 11: List of Data Displays](#). The AE analysis will include part 1 and part 2 in one display (Part 1 placebo and Part 2 placebo displayed separately) for summary tables and listings.

The following summaries will be provided:

- Adverse events overview
- All adverse events by SOC and PT and all adverse events by maximum grade and SOC and PT
- Drug related adverse events by SOC and PT and drug related adverse events by maximum grade and SOC and PT
- Serious Adverse Events by SOC and PT (Number of Participants and Occurrences)
- Adverse events leading to withdrawal from study/permanent discontinuation of study treatment
- Common ($\geq 5\%$) adverse events by overall frequency
- Common ($\geq 5\%$) non-serious adverse events (Number of Subjects and Occurrences)

The following listings will be provided:

- All adverse events
- Subject numbers for individual AEs
- Serious adverse events
- Drug related adverse events
- Adverse events leading to withdrawal from study/permanent discontinuation of study treatment
- Fatal serious adverse events
- Non-fatal serious adverse events

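### The single AE display counts all events to final follow-up, so Part 2 columns mix GSK3640254 monotherapy with cART, and the dose columns are not comparable across parts

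*SAP*

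**What the plan says.** SAP 13.4.2 (Treatment Emergent Flag for Adverse Events) sets the window as "Study Treatment Start Date ≤ AE Start Date ≤ Final Follow-up Visit". Protocol 9.2.1 gives the collection period: "All AEs will be collected from the start of treatment until the final follow-up visit". The two periods coincide.

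The final visit falls at different times. In Part 1 it is "approximately 8-14 days after the last dose" (Protocol Synopsis), and antiretrovirals are not started until it is complete. In Part 2 it is "3-5 days after the last dose". Protocol 5.1.1.2 has Part 2 participants start "cART immediately in the post-dosing period on Day 8, after the blood collection is performed", and Section 7.8 says this is done in the clinic. The instruction makes no exception for the placebo group.

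On layout, SAP 8.1 says: "The AE analysis will include part 1 and part 2 in one display". The placebo groups are shown separately by part. SAP 5.1 adds an overall column to all summaries.

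SAP 13.4.1 does define a separate Follow-up Period, "Study treatment stop date + 1 to Day 24 in Part 1 and study treatment stop date + 1 to Day 12 in Part 2". No AE table in SAP 8.1 or Appendix 11 is split by it, or by the start of cART.

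**The concern.** The first secondary objective is the safety and tolerability of GSK3640254 given alone, for 10 days in Part 1 and 7 days in Part 2. The study is dose-ranging and is meant to inform dose choice for Phase 2b, so readers will look across the dose columns of the AE table.

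Those columns differ in more than dose. The 10 and 200 mg columns (Part 1) carry a long window without antiretrovirals. The 40, 80 and 140 mg columns (Part 2) carry a shorter window whose last days are on a different regimen. The overall column pools the two. A gap between columns, or the lack of one, could come from follow-up time or cART rather than from dose.

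The laboratory tables raise a narrower question. They are reported by part, so unequal windows do not arise within a table. But chemistry and haematology are drawn in Part 2 at Visit 7, on cART, and the SAP is unclear whether the worst-case grade shifts include that visit.

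**Working it through.** **Inputs.** Last dose is Day 10 (Part 1) or Day 7 (Part 2). Final visit is 8-14 or 3-5 days later (Protocol Synopsis). First cART dose in Part 2 is on Day 8 (Protocol 5.1.1.2 and 7.8). Active arms have 6 participants each, and each part has 2 on placebo.

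**Reproducing the plan's figures.**
- Part 1: 10 + 8 = Day 18 to 10 + 14 = Day 24.
- Part 2: 7 + 3 = Day 10 to 7 + 5 = Day 12.
- With 28 days of screening, 28 + 24 = 52 and 28 + 12 = 40 days, matching the longest courses in the Synopsis. Protocol 5.1.1.2 agrees for Part 1, "the 9 required visits over the (maximum) 24-day study period", and gives a 12-day maximum for Part 2.

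**Window ratio (Part 1 ÷ Part 2).** 18/12 = 1.5; 18/10 = 1.8; 24/12 = 2.0; 24/10 = 2.4.

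**Share of the Part 2 window from Day 8 onward.** (10 − 7)/10 = 30%; (11 − 7)/11 = 36%; (12 − 7)/12 = 42%. This slightly overstates time on cART, because an AE early on Day 8 may precede the dose.

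**Illustration of unequal windows alone.** The documents give no AE rate for this population, so the hazard *h* is assumed constant, equal in both parts and unaffected by drug or cART. The proportion with at least one AE by day *d* is 1 − exp(−*hd*).

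| *h* per day | 24 days | 12 days | 7 days | Expected of 6: 24 vs 12 days |
|---|---|---|---|---|
| 0.01 | 21.3% | 11.3% | 6.8% | 1.3 vs 0.7 |
| 0.03 | 51.3% | 30.2% | 18.9% | 3.1 vs 1.8 |
| 0.05 | 69.9% | 45.1% | 29.5% | 4.2 vs 2.7 |

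Among Part 2 participants with an AE by Day 12, the share whose first event falls on or after Day 8 is 1 − 6.8/11.3 = 40%, 1 − 18.9/30.2 = 37% and 1 − 29.5/45.1 = 35%. This reflects elapsed time only; no cART effect is built in.

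**Alternative windows.** Cutting at the last dose gives 10 vs 7 days, a ratio of 10/7 = 1.43. A common Day 1-7 window gives a ratio of 1.0 and no cART time.

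**Drug still present after the last dose.** Protocol 3.2.2 gives a mean repeat-dose half-life of about 22-29 h in healthy participants. On a single-exponential approximation, 0.5^(24/22) = 47% to 0.5^(24/29) = 56% remains at 24 h, and 0.5^(120/22) = 2% to 0.5^(120/29) = 6% at 120 h. Events soon after the last dose are therefore relevant to the drug.

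**Laboratory text side by side.** SAP 8.3 limits the report of maximum-grade abnormalities worsened from baseline to those on treatment. The programming note to Tables 3.15 and 3.16 (chemistry grade shifts) asks for the worst of the post-baseline visits, which would take in Visit 7. The SAP does not define on-treatment for laboratory data. SAP 13.4.1 ends the Part 2 Treatment Period at Day 7 or the stop date.

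**The case against.** Much of the case on the other side stands.

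- The safety analysis is descriptive and no hypothesis is tested, so no cross-part comparison is formally planned.
- Following AEs past the last dose is defensible given the half-life.
- Within each part, active and placebo columns share the same window and the same planned cART exposure.
- Drug-related AEs have their own tables (3.6 and 3.7) and listing, and investigators must weigh concomitant therapy when judging cause. cART has its own table and listing (Table 3.57, Listing 31). With about 34 participants, events can be checked one by one.
- Laboratory values are also tabulated by visit, so Visit 7 can be seen separately.

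These points reduce the problem but leave it in the all-AE, common-AE, special-interest and SAE tables. Two placebo participants per part cannot separate a cART effect.

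A reader might infer three stronger things that the documents do not support. First, that the flag definition is the fault and changing it would repair the tables. The flag removes no collected AE, and the planned AE tables are titled for all events, so a new definition alone would change nothing in them. Second, that on-cART events are attributed to GSK3640254. They are counted in the randomised dose column, which is not a causal attribution. Third, that the worst-case laboratory tables certainly include on-cART values. SAP 8.3 points the other way, so this is an inconsistency to resolve.

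**Conclusion.** The point holds for the descriptive AE tables. As planned, 30-42% of the Part 2 AE window is Day 8 onward, when participants are on cART. The Part 1 window is 1.5 to 2.4 times as long, exactly 2 at the planned maxima, and has no antiretrovirals. The dose columns and the overall column therefore do not match the monotherapy objective and should not be compared across parts.

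The window lengths follow from the documents, assuming dosing and visits go to schedule. The AE percentages rest on an assumed hazard and should be read only as a range: 21-70% over 24 days against 11-45% over 12 days, or about 0.6 to 1.5 participants per arm of six. No test, error rate or sample size is affected. The documents also do not require demoting the all-events table: a cut at the last dose would still leave a 1.43-fold imbalance and would drop events while about half the drug remains a day later. This is a worthwhile, inexpensive improvement in presentation.

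**What to change.** Keep the all-events tables, and add the following from data already planned:

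1. Split the Part 2 AE summaries into before, and from, the first recorded cART dose. Split Part 1 into the Treatment and Follow-up Periods of SAP 13.4.1. State a rule for Day 8 events with no recorded time, since SAP 13.4.2 uses clock times only if collected.
2. Add a Day 1-7 AE summary for all dose groups and both placebo groups, and make it the basis for any cross-part or overall statement. Footnote the all-events tables with the window lengths and the Day 8 start of cART in Part 2.
3. Reconcile SAP 8.3 with the note to Tables 3.15 and 3.16, and apply the same basis to the haematology shifts (Tables 3.25 and 3.26). Report Part 2 Visit 7 values separately from the worst-case monotherapy shift. Say where Visit 6 belongs: it is drawn after the last study dose but before cART.

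The cost is SAP wording, a period variable and a few extra descriptive tables with small counts. The study phases are already defined, and the Part 2 schedule already has eCRF completion for the Day 8 cART dose. No new visit, sample or participant is needed.
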